RNA	Ribonucleic acid
SAE	Serious adverse event
SAP	Statistical analysis plan
SC	Subcutaneous
SCORAD	SCORing Atopic Dermatitis
SD	Standard deviation
SF-36v2	Short Form 36-item Health survey Version 2
SI	System international
CCI	
SoA	Schedule of Activities
SOC	System organ class
TEAE	Treatment-emergent adverse event
TBL	Total bilirubin
ULN	Upper limit of the normal
VAS	Visual analogue scale

AMENDMENT HISTORY

Category*: Change refers to	Date	Description of change	In line with the CSP?	Rationale
N/A – first version	20 November 2020			
2.0	16 May 2022		Yes	Updates aligned with protocol amendment
2.0	16 May 2022		Yes	Updates from TFL shell development and from comments received after blinded data reviews of outputs and datasets.

* Pre-specified categories are

Primary or secondary endpoints; Statistical analysis method for the primary or secondary endpoints; Derivation of primary or secondary endpoints; Multiple Testing Procedure; Data presentations; Other

1 STUDY DETAILS

This statistical analysis plan (SAP) outlines the analyses to be generated for the global clinical study report (CSR). Additional analyses required for regional submissions will be prespecified in a separate analysis plan and will be submitted to the appropriate authorities.

Table 1 Objectives and Endpoints

[figure not shown]
Objectives	Estimand description / Endpoints
Primary	
To compare the clinical efficacy of benralizumab 30 mg with placebo in patients with AD despite treatment with topical medications ^a .	
 • Population: Full analysis set • Endpoint: A binary response giving the proportion of patients with an IGA 0/1 and a decrease in IGA of ≥ 2 points at Week 16 relative to baseline • Intercurrent events: Patients who withdraw from the study will be considered as non-responders from the time of withdrawal up to Week 16. Patients who require rescue therapy from Day 29 up to Week 16 will be considered as non-responders from the time of this rescue use up to Week 16. • Summary measure: Odds ratio and difference in proportions between benralizumab and placebo at Week 16
Secondary	
To compare the effect of benralizumab with placebo on supportive measures of clinical efficacy in patients with AD despite treatment with topical medications ^a .	
 • Key secondary endpoint ^c: proportion of patients with skin clearance (EASI-75) at Week 16 • Key secondary endpoint ^c: proportion of patients with an improvement of ≥ 4 points in peak pruritus weekly score at Week 16 • Key secondary endpoint ^c: proportion of patients with skin clearance (EASI-90) at Week 16 • Proportion of patients with skin clearance (EASI-50) at Week 16 • Proportion of patients with skin clearance (EASI-100) at Week 16 • Change from baseline in EASI score at Week 16 • Change from baseline in peak pruritus score at Week 2 • Change from baseline in POEM score at Week 16 • Change from baseline in SCORAD at Week 16
To compare benralizumab with placebo on patient-reported health-related quality of life measures in patients with AD despite treatment with topical medications ^a .	
 • Change from baseline in DLQI and CDLQI at Week 16
To estimate the PK and immunogenicity of benralizumab 30 mg in in patients with AD despite treatment with topical medications ^a .	
 • Serum benralizumab concentration • ADA

Table 1 Objectives and Endpoints


To compare long-term treatment with benralizumab 30 mg Q8W versus benralizumab 30 mg Q4W up to Week 52 in patients with AD despite treatment with topical medications ^a.
	
 • Change from baseline in EASI total score at Week 52. • Proportion of patients with an IGA 0/1 and a decrease in IGA of ≥ 2 points at Week 52 relative to baseline • Proportion of patients with EASI-75 at Week 52 • Other supportive efficacy assessments at Week 52 as appropriate.

Safety
	

To compare the safety and tolerability of benralizumab with placebo in patients with AD despite treatment with topical medications ^a.
	
Safety and tolerability will be evaluated in terms of AEs, Vital signs, and Clinical laboratory values.
 
Assessments related to AEs cover:
 
 • Occurrence/frequency • Relationship to IP as assessed by Investigator • Intensity • Seriousness • Death • AEs leading to discontinuation of IP 
Vital signs parameters include systolic and diastolic blood pressure, and pulse, as well as respiration rate, body temperature, body weight, and height.
 
Assessments related to vital signs cover:
 
 • Observed value • Absolute and percent change from baseline values over time

Tertiary/exploratory
	

To explore the effect of benralizumab compared to placebo on healthcare resource utilization due to AD.
	
Rate of AD-related healthcare resource utilization during the study

To explore the effect of benralizumab compared to placebo on patient-reported health-related quality of life measures in patients with AD despite treatment with topical medications ^a.
	
Change from baseline in scores for:
 
 • HADS • PGI-S • SF-36v2 Health Survey (PCS and MCS) • EQ-5D-5L 
Observed scores for:
 
 • CCI [REDACTED] • Patient-reported experience (free text entry)

CCI [REDACTED]
	

Table 1 Objectives and Endpoints

CCI

- ^a The locally-approved regimen of topical medication.
- ^b Rescue therapy is defined in CSP Section 6.5.3.
- ^c The key secondary endpoints will use the same estimand as outlined for the primary endpoint. For all other endpoints, the estimands will be detailed in the SAP.

CCI AD, Atopic dermatitis; ADA, anti-drug antibodies; AE, adverse event; CDLQI, The Children's Dermatology Life Quality Index; CSP, Clinical study protocol; DLQI, Dermatology Life Quality Index; EASI, Eczema Area and Severity Index; EQ-5D-5L, European Quality of Life-5 Dimensions; HADS, Hospital Anxiety and Depression Scale; IGA, Investigator Global Assessment; IP, investigational product; CCI PGI-S, Patient Global Impression of Severity; PK, pharmacokinetics; POEM, Patient Oriented Eczema Measure; Q4W, every 4 weeks; Q8W, every 8 weeks; CCI CCI SAP, Statistical Analysis Plan; SCORAD, SCORing Atopic Dermatitis; SF-36v2, Short Form 36-item Health Survey Version 2; CCI

1.1 Study design

1.1.1 Overall Design

This is a Phase 2 multinational, randomized, double-blind, parallel-group, 16-week placebo-controlled study with a 36-week extension. The study will evaluate the efficacy and safety of benralizumab 30 mg in male and female participants ≥ 12 years of age with moderate to severe atopic dermatitis (AD) who remain symptomatic despite treatment with standard of care treatment with topical medications. At this time adolescent participants will not be enrolled in sites in the United States. Adolescents may be recruited when and where approval is granted. The study is designed to assess the safety and efficacy of benralizumab 30 mg compared with placebo and identify the appropriate maintenance administration frequency (every 4 weeks (Q4W) versus every 8 weeks (Q8W)).

This study consists of the following consecutive periods:

- A 1- to 4-week run-in period, including a 7-day washout period of topical medications prior to randomization;
- A 16-week placebo-controlled, double-blind treatment period;

- A 36-week blinded-to-dosing regimen extension period for maintenance treatment.

[figure not shown]
Following informed consent, all eligible participants will enter a run-in period of 1 to 4 weeks during which inclusion/exclusion criteria will be assessed, medical history taken, and complete physical exam will be conducted (Visit 1, CSP Table 3). Potentially eligible participants will enter a 7-day washout period during which all topical medications for AD except the stable emollient moisturizer regimen must be discontinued. Participants will be provided with a handheld device to respond to patient-reported outcome (PRO) questionnaires during the study.

Following the 1- to 4-week run-in period, including the 7-day washout period, a minimum of approximately 160 participants will be randomized at Visit 2, in a ratio of 1:1:2, respectively, to 1 of the following 3 treatment sequences (see also [Figure 1](#) and [Figure 2](#)):

- Benralizumab 30 mg Q4W until Week 16, followed by an extension period with benralizumab 30 mg Q4W administered until Week 52 (n = 40);
- Benralizumab 30 mg Q4W until Week 16, followed by an extension period with benralizumab 30 mg Q8W administered until Week 52 (n = 40);
- Placebo Q4W until Week 16, followed by an extension period with benralizumab 30 mg Q4W administered until Week 28, and then benralizumab 30 mg Q8W administered until Week 52 (n = 80).

[Figure 1](#) presents an overview of investigational product (IP) administration for each randomized treatment group.

Figure 1 Investigational Product Administration Q4W by Randomized Treatment Sequence

^a In the extension phase, participants will receive benralizumab on a Q8W or Q4W dosing regimen, as predetermined at randomization (Visit 2). Participants randomized to receive benralizumab Q8W in the extension phase will also receive placebo at intervening study visits when they are not receiving benralizumab.

Q4W, every 4 weeks; Q8W, every 8 weeks.

All participants who prematurely discontinue IP (IPD) should return to the study site for the IPD visit 4 weeks (± 7 days) after the last dose of IP for procedures, or as soon as feasible if this interval is missed (eg, if decision on discontinuation was made later), as specified in Table 3 of the CSP.

[figure not shown]
At the IPD visit, the participant will be offered the following options for further follow-up:

- Participants are encouraged to return to all scheduled site visits and perform all procedures but without IP administration, until the end of the study (Visit 16).
- Participants unwilling or unable to attend the scheduled site visits until the end of the double-blind treatment period, will be offered a follow-up option that includes monthly telephone contact instead. During follow-up telephone contact, the Investigator will collect information about concomitant medications, information on AD symptoms, and AE/SAE(s).

All Week 16 analyses at primary database lock (DBL) will evaluate the two initial dose treatment arms: benralizumab 30 mg (total $n = 80$), and placebo (total $n = 80$). Analyses of data for Week 52 end of study reporting will include data from the entire study, presenting the three randomized treatment groups: benralizumab followed by Q4W, benralizumab followed by Q8W and placebo followed by benralizumab Q4W-Q8W.

For an overview of the study design, see [Figure 2](#). For further details see CSP Section 4.1.

Figure 2 Study Design

^a To maintain blinding, participants will receive investigational product every Q4W during the extension period. Placebo will be administered Q8W, occurring 4 weeks after each benralizumab administration. n, number; Q4W, every 4 weeks; Q8W, every 8 weeks.

Participants and Investigators will remain blinded to the treatment and regimen until the final DBL.

1.1.2 Investigational Product Dosing Regimen

Participants who meet entry criteria will be randomized 1:1:2 by the interactive voice/web response system (IxRS) to 1 of the 3 treatment sequences described in Section 1.1.

Blinded IP (benralizumab or placebo) will be administered Q4W at Weeks 0, 4, 8, and 12 (Figure 1).

From Week 16 onwards, participants initially randomized to benralizumab 30 mg will receive benralizumab 30 mg Q4W or Q8W interval, according to their original randomization at Visit 2 (Week 0) (Figure 1).

At Weeks 16, 20, and 24, participants initially randomized to placebo will receive benralizumab 30 mg Q4W. At Week 28, these participants will transition to receive benralizumab 30 mg Q8W interval (Figure 1).

All participants on Q8W regimen from Week 16 onwards will continue to receive treatment containing placebo at their Q4W visit intervals (Figure 1), thus maintaining the blinded treatment regimen.

The final dose of benralizumab or placebo will be administered at Week 48.

Please refer to the clinical study protocol (CSP) for more details.

1.2 Number of participants

Approximately 270 participants are expected to be enrolled/screened in order to achieve at least 160, and a maximum of 200, eligible study participants randomly assigned to study intervention to ensure that a broad distribution of participants is recruited across the range of ages and blood eosinophil levels to allow potential identification of responding subpopulations and appropriate cut-offs for future studies, if necessary.

Randomization will be stratified by blood eosinophils (< 300 cells/ μ L, ≥ 300 cells/ μ L) collected at screening and age at screening (≥ 12 to < 18 years and ≥ 18 years). Participants will be randomized in minimum cohort sizes across the baseline blood eosinophil and age subgroups; the intended distribution of participants in total across the treatment groups for each combination of these factors is summarized in Table 2. If the minimum recruitment target in any cohort is achieved, that cohort may remain open in order to fulfil minimum recruitment targets for the remaining cohorts. Thus, minimum recruitment targets may be exceeded in cohorts that remain open while fulfilling recruitment targets for other cohorts. Recruitment will stop when a maximum of 200 participants in total is achieved.

Table 2 Number of Participants Randomized by Stratification Factors

	Baseline blood eosinophils	
	<300 cells/ μ L	\geq 300 cells/ μ L
Adolescents (\geq 12 to < 18 years), n	20	30
Adults (\geq 18 years), n	40	70

For the primary analysis in the overall population, a minimum of 80 participants per treatment group will provide a high level of power (> 95%) to detect a 30% difference between benralizumab 30 mg Q4W and placebo for the primary endpoint. This calculation is based on a 2-sided test and a 5% significance level and assumes a response rate of 40% for benralizumab 30 mg Q4W and 10% for placebo.

For subgroup analyses, a minimum of 35 participants per treatment group will provide at least 80% power to detect a 30% difference between benralizumab 30 mg Q4W and placebo (using the same assumptions as for the primary analysis). Thus, there is a high probability of detecting differences between treatments at the 2-sided 5% level in the baseline blood eosinophils \geq 300 cells/ μ L subgroup (with 50 participants per treatment) and in the adult subgroup (with 55 participants per treatment). In addition, there is a high chance of demonstrating statistical significance at the 2-sided 10% level in the adolescent subgroup (with 25 participants per treatment). Note that in the baseline blood eosinophils < 300 cells/ μ L subgroup, 30 participants per treatment group will provide an adequate amount of data to explore treatment differences, and will allow different cut-offs between ‘low’ and ‘high’ eosinophils at baseline to be assessed.

2 ANALYSIS SETS AND PERIODS

2.1 Definition of study analysis periods

The first set of analyses will be run after the primary DBL, which will occur after all randomized participants have completed the initial 16-week treatment period or discontinued prior to Week 16.

For Week 16 analyses, all data over the entire 16-week placebo-controlled treatment period (or last dose in placebo-controlled period + 30 days for those who do not enter the extension period) will be included in the analyses. Descriptive by-visit summaries and data listings will be presented for all available data for the entire study. Additionally, a limited number of key summaries may be presented for the entire 52-week treatment period including all available data.

Analyses for the first 16 weeks will compare the two initial treatment groups, benralizumab 30 mg Q4W Total and placebo Q4W. Summaries will also display the randomized treatment sequences (benralizumab 30 mg Q4W/Q4W, benralizumab 30 mg Q4W/Q8W).

The final set of analyses will be produced at the final DBL, which will occur when all participants have completed the 52-week treatment period and/or the IPD/EOT/Week 60 follow-up visit.

For Week 52 reporting, all data over the entire 52-week treatment period (and Week 60 follow-up visit and/or IPD/EOT visit) will be presented in the analyses, summaries, and data listings. Additionally, some summaries will be presented only on data from the extension period.

The start of the extension period is defined as starting after the date/time of first dose of IP in the extension period (Week 16 IP administration), ie assessments at Week 16 visit will be included into the Week 16 reporting.

Analyses for the Week 52 reporting will be presented by the 3 randomized treatment sequences (benralizumab 30 mg Q4W/Q4W, benralizumab 30 mg Q4W/Q8W and placebo/benralizumab). Summaries from baseline to Week 52 will also display the initial benralizumab 30 mg Q4W Total group.

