3.4.1 Adverse Events

AEs (including SAEs) experienced by the participants will be collected throughout the entire study and will be coded using the latest version of the Medical Dictionary for Regulatory Activities (MedDRA) that will have been released for execution at AstraZeneca/designee per the Data Management Plan.

AEs for the 16-week placebo-controlled analysis reporting will include all AEs with start date prior to entering the extension period.

AEs for the Week 52 end of study reporting over the entire study duration will include all AEs as defined below. AEs reported for the extension period alone are those with start date on or after the date of first dose of treatment during the extension period.

As per CSP Section 9.4.3, the following events are considered treatment emergent:

- AEs with an onset date on or after the first dose of IP;
- Worsening of pre-existing events on or after first dose of IP.

For the analysis, an AE will be defined as Treatment Emergent AE (TEAE) if it has an onset date on or after the first dose of IP. Applying this definition, also the worsening of pre-existing events on or after the first dose of IP will be included in the analysis as Investigators are instructed to record these as new events.

AE data will be categorized according to their onset date into the following study periods:

- AEs in the pre-treatment period are defined as those with an onset prior to the day of first dose of IP.
- AEs in the on-treatment period for 16-week placebo-controlled period are defined as those with onset date between day of first dose of IP and the day prior to first dose in extension period; or the last dose in placebo-controlled period + 30 days for those who do not enter the extension period.
- AEs in the on-treatment period for extension period only are defined as those with onset date between day of first dose of IP in the extension and the last dose + 30 days.
- AEs in the on-study period for Week 52 end of study reporting are defined as those with onset on or after the day of first dose of IP.

If an AE has a missing onset date then unless the stop date of the AE indicates otherwise, this will be considered an on-treatment AE. Similarly, if an AE has a partial onset date, then unless

the partial onset date or the stop date indicates otherwise, this will be considered an on-treatment AE.

AEs that have missing causality (after data querying) will be assumed to be related to study drug.

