4 ANALYSIS METHODS

The primary DBL is targeted to occur when all participants have completed the 16-week placebo-controlled treatment period. The final DBL will occur when all participants have completed the 52-week treatment period and the Week 60 follow-up visit and/or the IP discontinuation (IPD) /EOT visit.

All data will be included in the analyses, regardless of whether IP was prematurely discontinued or delayed, and irrespective of protocol adherence, unless the participant withdrew consent to further study participation.

All personnel involved in the analyses of the study will remain blinded until the primary DBL and protocol deviations are identified.

The CSR will be based on the final DBL.

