Continuous data will be summarized with descriptive statistics of number of available observations, mean, standard deviation (SD), median, minimum and maximum, and quartiles where more appropriate. Mean and median will be reported to one decimal place more than the data recorded, the SD to one decimal place more than the mean, other items to the precision recorded (maximum rounded to 4 decimal places). Data listings will be sorted by treatment and participant number.

All point estimates will be presented together with 95% confidence intervals (CIs) as measures of precision and nominal 2-sided p-values, rounded to 4 decimal places.

For Week 16 analyses, all data over the entire 16-week placebo-controlled treatment period (or last dose in placebo-controlled period + 30 days for those who do not enter the extension period) will be presented in summaries and data listings (see Section 2.1).

For Week 52 end of study reporting, all data over the entire 52-week treatment period (and Week 60 follow-up visit and/or IPD/EOT visit) will be presented in summaries and data listings (see Section 2.1).

Analyses for the first 16 weeks will compare the two initial treatment groups, benralizumab 30 mg Q4W Total and placebo Q4W. Summaries will also display the randomized treatment sequences (benralizumab 30 mg Q4W/Q4W, benralizumab 30 mg Q4W/Q8W).

Analyses for the Week 52 end of study reporting will be presented by the 3 randomized treatment sequences (benralizumab 30 mg Q4W, benralizumab 30 mg Q8W and placebo/benralizumab), as noted in Section 1.1.1. Summaries will also display the initial benralizumab 30 mg Q4W Total group. For efficacy analyses, the Q4W versus Q8W dosing regimen will be statistically compared for participants originally randomized to benralizumab 30 mg Q4W initial dose, with all data (including placebo/benralizumab group) included in the model.

Additionally, a small number of key efficacy and safety tables will also be presented for data in the extension period alone to explore where a direct comparison of Q4W versus Q8W dosing can be made for participants previously receiving benralizumab, and to summarize time on benralizumab alone for participants previously receiving placebo. Adverse events will be presented for each period separately and only overall for key tables.

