The data analyses will be conducted using the SAS® System (SAS Institute Inc., Cary, NC). All SAS® programs used to generate analytical results will be developed and validated according to AstraZeneca SAS® programming standards and validation procedures.

Table 11 Primary and key secondary efficacy and main safety estimands

Statistical Category	Estimand ^a				Section
	Treatment Condition ^a	Endpoint (Population)	Intercurrent Event Strategy ^a	Population Level Summary ^a (Analysis)	
Primary Objective: To compare the clinical efficacy of benralizumab 30 mg with placebo in patients with AD despite treatment with topical medications					
Primary	Treatment with benralizumab versus placebo, regardless of compliance, where rescue from Day 29 indicates treatment failure	
 • A binary response giving the proportion of patients with an IGA 0/1 and a decrease in IGA of ≥ 2 points at Week 16 relative to baseline (FAS) 	
 • All data up to Week 16 will be included • Treatment discontinuation – treatment policy • Rescue medication from Day 29 onwards – non-responders • Withdrawal from study – non-responders 	
 • Odds ratio, with corresponding 95% CIs (logistic regression) 	4.2.6.1
Key secondary objective: To compare the effect of benralizumab with placebo on supportive measures of clinical efficacy in patients with AD despite treatment with topical medications					
Key secondary	Treatment with benralizumab versus placebo, regardless of compliance, where rescue from Day 29 indicates treatment failure	
 • Proportion of patients with skin clearance (EASI-75) at Week 16 (FAS) • Proportion of patients with an improvement of ≥ 4 or more points in peak pruritus weekly score at Week 16 (FAS) • Proportion of patients with skin clearance (EASI-90) at Week 16 (FAS) 	
 • All data up to Week 16 will be included • Treatment discontinuation – treatment policy • Rescue medication from Day 29 onwards – non-responders • Withdrawal from study – non-responders 	
 • Odds ratio, with corresponding 95% CIs (logistic regression) 	4.2.7.1, 4.2.7.2
Safety Objective: To compare the safety and tolerability of benralizumab with placebo in patients with AD despite treatment with topical medications					

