Safety	Treatment with benralizumab versus placebo, regardless of rescue medication	
 • Presence of TEAEs through EOT (safety) • Presence of serious TEAEs through EOT (safety) 	Remained adherent to intervention (on-treatment)	
 • Categorical descriptive 	4.2.8

^a All estimand attributes explicitly identified for primary and key secondary estimands only.

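### The Week 16 cut-off at last dose + 30 days is not limited to safety and, for efficacy, contradicts the treatment-policy estimand

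*SAP*

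**What the plan says.** **Where the cut-off stands.** Section 2.1, which defines the analysis periods, gives the Week 16 analysis data as everything over the 16-week placebo-controlled period, "or last dose in placebo-controlled period + 30 days for those who do not enter the extension period) will be included in the analyses". Section 4.1 repeats the limit for output: data to last dose + "30 days for those who do not enter the extension period) will be presented in summaries and data listings". Neither sentence mentions safety. Section 2.1 also says: "Descriptive by-visit summaries and data listings will be presented for all available data for the entire study".

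**Where the cut-off belongs.** Section 3.4.1 ends the on-treatment adverse-event period for the 16-week phase with the same words: "or the last dose in placebo-controlled period + 30 days for those who do not enter the extension period". In Table 11 only the safety row carries an on-treatment strategy: "Remained adherent to intervention (on-treatment)".

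**What the SAP says for efficacy.**
- Table 11, primary and key secondary rows: "All data up to Week 16 will be included", and "Treatment discontinuation – treatment policy".
- Section 4: "All data will be included in the analyses, regardless of whether IP was prematurely discontinued or delayed"; the exception is withdrawal of consent.
- Section 4.1, Week 16 rules: records become non-response or missing only through rescue from Day 29, study withdrawal or a missed visit.
- Section 4.2.6.1: the intercurrent events are study withdrawal and rescue. Stopping IP is not one of them.
- Appendix 8.1.3: the MMRM uses data to study withdrawal or Week 16, whichever comes first, whether or not IP was stopped.

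**The concern.** The two sets of rules give different answers for the same record: the Week 16 assessment of a participant who stopped IP early but stayed in the study. Section 2.1 excludes it once more than 30 days have passed since the last dose. The efficacy rules keep it.

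The SAP plans for such participants. Section 1.1.1 encourages those who stop IP to attend all remaining visits without dosing, and Section 4.2.1 counts those who stop IP but complete follow-up. Section 2.2.5 requires a dose of benralizumab after Week 16 for extension entry, so early IP discontinuers do not enter the extension and fall under the 30-day clause.

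If a programmer applied Section 2.1 as written, an observed off-treatment responder would be counted as a non-responder for IGA, EASI-75, EASI-90 and peak pruritus, and a continuous score would be set to missing. The analysis would then penalize stopping IP, which the treatment-policy strategy in Table 11 is meant to avoid. No sentence in the SAP says which rule takes precedence.

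**Working it through.** **The plan's own figure.** Section 1.2 states power above 95% for 80 per group, 40% versus 10%, two-sided 5%. A two-proportion calculation gives 0.995, which agrees. Power is not in dispute. The question is which records enter the analysis.

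**Inputs.** Doses are given at Weeks 0, 4, 8 and 12 (Section 1.1.2). Section 3.1.3 places Week 4 on Day 29, so study day = 7 × week + 1, and Week 16 is Day 113. The Week 16 peak pruritus score uses Days 106 to 112 (Section 3.1.3) and needs at least 4 of 7 daily scores (Section 3.3.2). I assume that the first dose falls on the day of randomization (Day 1) and that dosing is on schedule.

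**Cut-off = day of last dose + 30.**

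| Last dose | Dose day | Cut-off | Days from cut-off to Day 113 | Days from cut-off to Day 106 | Pruritus days kept |
|---|---|---|---|---|---|
| Week 0 | 1 | 31 | 113 − 31 = 82 | 106 − 31 = 75 | 0 of 7 |
| Week 4 | 29 | 59 | 113 − 59 = 54 | 106 − 59 = 47 | 0 of 7 |
| Week 8 | 57 | 87 | 113 − 87 = 26 | 106 − 87 = 19 | 0 of 7 |
| Week 12 | 85 | 115 | 113 − 115 = −2 | 106 − 115 = −9 | 7 of 7 |

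For a last dose at Week 8 or earlier, both the Week 16 visit and the whole pruritus window lie after the cut-off. A last dose at Week 12 keeps an on-schedule visit with two days to spare. The IPD visit in Section 1.1.1 is due 4 weeks ± 7 days after the last dose, here Day 85 + 28 ± 7 = Days 106 to 120. An in-window visit on Days 116 to 120 would therefore also be cut.

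**Could the bracket only lengthen the period?** That reading works for a last dose at Week 12 (Day 115 against Day 113). For the other three dosing weeks the stated end precedes Week 16, and Section 3.4.1 uses the same words as an end point.

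**Size per participant.** Randomization is 1:1:2 with the two benralizumab sequences pooled, so 160 randomized gives 80 per arm and 200 gives 100. One observed responder recoded as a non-responder moves the arm's rate by 1/80 = 1.25 points or 1/100 = 1.0 point.

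**Illustration only.** The SAP gives no rate of stopping IP. Assume that 5% to 20% per arm stop by Week 8, attend Week 16 and respond at their arm's planned rate. Among the combinations tried:
- Smallest loss, 5% on benralizumab and 15% on placebo: 0.40 × 0.95 − 0.10 × 0.85 = 0.380 − 0.085 = 0.295.
- Largest loss, 20% on benralizumab and 10% on placebo: 0.40 × 0.80 − 0.10 × 0.90 = 0.320 − 0.090 = 0.230.

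The planned 30-point difference would be estimated as 29.5 to 23 points, with power of about 0.996 to 0.957. These figures rest on the assumed rates and are not a forecast.

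**The case against.** The strongest reply is that the record-level rules already settle the matter. Table 3 in Section 3.1.5 keeps a recorded responder as such unless rescue has been taken, and it has no category for a response recorded more than 30 days after the last dose. Section 3.1.3 builds windows so that each observation falls into a visit, and limits the 16-week windows only by extension entry. Days 106 to 112 are to be used for pruritus subject to the same limit. Endpoint-specific rules would ordinarily prevail over a general sentence on reporting periods. In addition, the Section 4.1 sentence concerns only summaries and listings, and the practical effect is narrow. A binary result changes only for a participant who stopped early, stayed in the study, had no rescue from Day 29 and was an observed responder. For IGA and EASI the participant must also have attended the site, while Section 1.1.1 offers telephone follow-up as an alternative.

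Much of this stands. The intended rule is clear, the direct conflict with the estimand lies in Section 2.1, and Section 4.1 adds an inconsistency in what is tabulated and listed. But Table 3 and Section 3.1.3 do not cure Section 2.1. They are two more rules that it contradicts. The section that defines the analysis periods still states a cut-off for the data in the analyses, and nothing subordinates it to the efficacy rules.

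**Conclusion.** The SAP is wrong as written on this point, at minor severity. For participants who do not enter the extension, Section 2.1 ends Week 16 data before the Week 16 visit whenever the last dose was at Week 8 or earlier. This is incompatible with the treatment-policy estimand and with every efficacy-specific rule in the document. If it were followed, each affected observed responder would cost the arm 1.0 to 1.25 percentage points.

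The number of such participants, and so the total size and direction of any bias, cannot be derived from the SAP. The day counts assume on-schedule dosing from Day 1. Participants with rescue from Day 29 are non-responders under either rule, so their binary results do not change. The rest of the SAP makes it unlikely that the cut would be applied to efficacy in practice.

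**What to change.** - In Sections 2.1 and 4.1, restrict the 30-day clause to the on-treatment safety reporting defined in Section 3.4.1.
- State in the same place that Week 16 efficacy analyses and summaries use all assessments up to Week 16 or study withdrawal, whichever is earlier, regardless of IP discontinuation or extension entry. Leave the rescue handling in Section 3.1.5 as it is.
- Align the two sections on descriptive output. Section 2.1 promises by-visit summaries and listings of all data from the entire study, while Section 4.1 applies the 30-day limit to Week 16 summaries and listings. If these are different output sets, say so.

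The cost is about two sentences of SAP wording, with no new data and no protocol change. Sample size and planned power are unaffected.
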